**Acceptable contraception methods are:**

- Total sexual abstinence (abstinence must be for the total duration of the trial and the follow-up period)
- Vasectomized sexual partner plus male condom (with participant assurance that partner received post-vasectomy confirmation of azoospermia)
- Tubal occlusion plus male condom
- Intra-uterine device – provided coils are copper-banded, plus male condom
- Intra-uterine system (IUS) levonorgestrel IUS (e.g., Mirena), plus male condom
- Medroxyprogesterone injections (Depo-Provera) plus male condom
- Etonogestrel implants (e.g., Implanon, Norplant) plus male condom
- Normal and low dose combined oral contraceptive pills, plus male condom
- Norelgestromin/ethinylestradiol transdermal system plus male condom
- Intravaginal device (e.g., ethinylestradiol and etonogestrel) plus male condom
- Cerazette (desogestrel) plus male condom (Cerazette is currently the only highly efficacious progesterone based pill)

**Unacceptable Contraception Methods**

The following methods are considered not to be highly effective and are therefore not acceptable contraceptive methods:

- Triphasic combined oral contraceptives
- All progesterone only pills except, Cerazette
- All barrier methods, if intended to be used alone
- Non-copper containing intra-uterine devices
- Fertility awareness methods
- Coitus interruptus

14. Men with a female partner of childbearing potential must have either had a prior vasectomy agree to use effective contraception as described in the full protocol for at least 14 days prior to administration of the first dose of study treatment, during the study, and for 120 days following the last dose of osimertinib. Men also can not donate sperm within this time period.

### 3.3.2 Exclusion Criteria

Any of the following criteria will exclude patients from study participation:

1. Leptomeningeal carcinomatosis or other CNS metastases.
2. Stage IIIB, or distant metastases (including malignant pleural effusion) identified on PET-CT scan or biopsy (PET abnormalities that are negative for malignancy on biopsy will be considered on a case by case basis).
3. Past medical history of ILD, drug-induced ILD, radiation pneumonitis which required steroid treatment, or any evidence of clinically active ILD.
4. Patients who are known to be serologically positive for human immunodeficiency virus (HIV)
5. Active second malignancy, i.e. patient known to have potentially fatal cancer present for which he/she may be (but not necessarily) currently receiving treatment. Patients with a

- history of malignancy that has been completely treated, with no evidence of that cancer currently, are permitted to enroll in the trial provided all chemotherapy for prior malignancy was completed >12 months prior and/or bone marrow transplant >2 years prior.
6. Patients who are currently receiving treatment with contraindicated QTc prolonging medications or potent CYP3A4 inducers (at least 3 weeks prior) (Appendix 6), if that treatment cannot be either discontinued or switched to a different medication prior to first day of study treatment. Listing of contraindicated QTc prolonging and CYP3A4 inducing/inhibiting medications is provided in Tables 4.1, 4.2, and 4.3, with washout periods. All patients must try to avoid concomitant use of any medications, herbal supplements and/or ingestion of foods with known inducer effects.
  7. Any of the following cardiac abnormalities or history:
    - Mean resting corrected QT interval (QTc) >470 msec, obtained from 3 electrocardiograms (ECGs), using the screening clinic ECG machine derived QTc value.
    - Any clinically important abnormalities in rhythm, conduction or morphology of resting ECG e.g. complete left bundle branch block, third degree heart block and second degree heart block.
    - Any factors that increase the risk of QTc prolongation or risk of arrhythmic events such as heart failure, electrolyte abnormalities (including: Serum/plasma potassium < LLN; Serum/plasma magnesium < LLN; Serum/plasma calcium < LLN), congenital long QT syndrome, family history of long QT syndrome or unexplained sudden death under 40 years of age in first degree relatives or any concomitant medication known to prolong the QT interval.
  8. Treatment with prohibited medications (concurrent anticancer therapy including chemotherapy, radiation, hormonal treatment [except corticosteroids and megestrol acetate], or immunotherapy) ≤ 14 days prior to treatment with osimertinib.
  9. Any evidence of severe or uncontrolled systemic diseases, including uncontrolled hypertension and active bleeding diatheses, which in the investigator's opinion makes it undesirable for the patient to participate in the trial or which would jeopardize compliance with the protocol, or known active infection including chronic active hepatitis B virus (HBV), hepatitis C virus, and HIV. Screening for chronic conditions is not required. Patients with chronic HBV with negative HBV viral load on appropriate antiviral therapy will be permitted, if able to continue appropriate antiviral therapy throughout treatment period.
  10. Active tuberculosis.
  11. Signs or symptoms of infection within 2 weeks prior to first day of study.
  12. Therapeutic oral or IV antibiotics within 2 weeks prior to first day of study treatment:
    - Patients receiving prophylactic antibiotics (e.g., to prevent a urinary tract infection or chronic obstructive pulmonary disease exacerbation) are eligible.
  13. Class II to IV heart failure as defined by the New York Heart Association functional classification system.
  14. Patients with known coronary artery disease, congestive heart failure not meeting the above criteria, or LVEF <50% must be on a stable medical regimen that is optimized in the opinion of the treating physician, in consultation with a cardiologist if appropriate, to be eligible.
  15. Patients who have experienced untreated and/or uncontrolled cardiovascular conditions and/or have symptomatic cardiac dysfunction (unstable angina, congestive heart failure, myocardial infarction within the previous 3 months; coronary angioplasty, or stenting or bypass grafting within the past 6 months; cardiac ventricular arrhythmias requiring medication; any history of 2nd or 3rd degree atrioventricular conduction defects);

16. Females who are pregnant or breastfeeding;
17. Presence of active gastrointestinal (GI) disease (including GI bleeding or ulceration) or other condition that could affect GI absorption (e.g., malabsorption syndrome, history of biliary tract disease), including refractory nausea or vomiting, or chronic GI disease which may affect absorption or tolerance to oral medications.
18. History of hypersensitivity to active or inactive excipients of osimertinib or drugs with a similar chemical structure or class to osimertinib.
19. Involvement in the planning and/or conduct of the study (applies to both Investigator staff and/or staff at the study site).
20. Participation in another clinical study with an investigational product (IP) during the last 3 months or within five half-lives of the compound, whichever is longer.
21. Uncontrolled medical, psychological, familial, sociological, or geographical conditions that interfere with the patient's safety, ability to provide informed consent, or ability to comply with the protocol.

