**Table 4.1 Drugs prolonging the QT interval**

Contraindicated drug	Withdrawal period prior to osimertinib start
Clarithromycin, droperidol, erythromycin, procainamide, aclarubicin, anagrelide, ciprofloxacin, cocaine, levofloxacin, ondansetron, papaverine hydrochloride, sulpiride, sultropride, terfenadine terlipressin	2 days
Cisapride, disopyramide, dofetilide, domperidone, ibutilide, quinidine, sotalol, sparfloxacin, thioridazine	7 days
Bepidil, chlorpromazine, halofantrine, haloperidol, mesoridazine	14 days
Levomethadyl, methadone, pimozide	4 weeks
Arsenic trioxide	6 weeks*
Pentamidine	8 weeks
Amiodarone, chloroquine	1 year

\*Estimated value as PKs of arsenic trioxide has not been studied

Metabolism of osimertinib is primarily carried out by CYP3A4/5. A drug-drug interaction study of osimertinib evaluated in patients showed that there is potential for osimertinib being a victim when co-administered with strong inducers of CYP3A4 (osimertinib concentrations are decreased when co-dosed with rifampicin)

The following potent inducers of CYP3A4 must not be used during this study for any patient receiving osimertinib.

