**Table 4.2 Drugs inducing CYP3A4**

Contraindicated drugs	Withdrawal period prior to osimertinib start
Carbamazepine, phenobarbital, phenytoin, rifampicin, rifabutin, rifapentine	3 weeks
St John's Wort	
Phenobarbitone	5 weeks

This list is not intended to be exhaustive, and a similar restriction will apply to other agents that are known to strongly modulate CYP3A4 activity. Appropriate medical judgment is required.

Osimertinib and its metabolites are substrates for P-gp and BCRP. Osimertinib may increase the concentration of sensitive BCRP and Pgp substrates (concentration of the sensitive BCRP substrate, rosuvastatin and sensitive Pgp substrate, fexofenadine, are increased).

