### **Drugs with a known risk of TdP**

Drug name	Withdrawal period prior to study treatment start

Aclarubicin, anagrelide, ciprofloxacin, clarithromycin, cocaine, droperidol, erythromycin, levofloxacin, ondansetron, papaverine hydrochloride, procainamide, sulpiride, sultopride, terfenadine terlipressin	2 days
Cilostazol, Cisapride, disopyramide, dofetilide, domperidone, flecainide, gatifloxacin, grepafloxacin, ibutilide, moxifloxacin, oxaliplatin, propofol, quinidine, roxithromycin, sevoflurane, sotalol, sparfloxacin, thioridazine	7 days
Azithromycin bepridil, citalopram, chlorpromazine, dronedarone, escitalopram, fluconazole, halofantrine, haloperidol, levomepromazine, levosulpiride, mesoridazine	14 days
Donepezil, terodiline	3 weeks
Levomethadyl, methadone, pimozone	4 weeks
Arsenic trioxide*, Ibogaine	6 weeks
Pentamidine	8 weeks
Astemizole, Probucole, vandetanib	4 months
Amiodarone, chloroquine	1 year

\* Estimated value as pharmacokinetics of arsenic trioxide has not been studied

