### **Other TdP risk Categories**

Patients receiving drugs that prolong QT interval or may increase the risk of TdP from other TdP risk categories can be enrolled, notwithstanding other exclusions and restrictions, if these drugs are considered essential for patient management and the patient has been stable on therapy. Close monitoring with ECGs and electrolytes is recommended.

Patients with congenital long QT syndrome (CLQTS) are excluded from this study.

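### Exclusion 6 takes its washout periods from Table 4.1, which omits 22 of the 58 known-TdP drugs given a washout in section 6.5; after other exclusions, the time off drug stays open for about 16

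*Combined protocol and SAP*

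**What the plan says.** Section 3.3.2, criterion 6, excludes patients receiving "contraindicated QTc prolonging medications or potent CYP3A4 inducers (at least 3 weeks prior) (Appendix 6") if that treatment cannot be stopped or switched before the first day of study treatment. It then says: "Listing of contraindicated QTc prolonging and CYP3A4 inducing/inhibiting medications is provided in Tables 4.1, 4.2, and 4.3, with washout periods".

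Table 4.1 (section 4.1.1) gives QT-prolonging drugs with withdrawal periods. Its 7-day row is "Cisapride, disopyramide, dofetilide, domperidone, ibutilide, quinidine, sotalol, sparfloxacin, thioridazine" and its 14-day row is "Bepidil, chlorpromazine, halofantrine, haloperidol, mesoridazine". Section 6.5 has a second table, for drugs with a known risk of TdP, with longer 7-day and 14-day rows and further rows that Table 4.1 lacks, such as 3 weeks for "Donepezil, terodiline". Nearly identical text introduces the two tables. Each introduction requires the drugs to be stopped before osimertinib starts, as set out in a Table 3, and no table of that number appears in the protocol.

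Appendix 6 lists prohibited drugs by name, without washouts. Table 4.3, which criterion 6 also cites, permits its drugs with caution and gives no washout.

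Criterion 7 excludes patients with factors that raise QTc risk, including "any concomitant medication known to prolong the QT interval". Section 6.5, under Other TdP risk Categories, says of patients who take such drugs from the remaining groups that they "can be enrolled, notwithstanding other exclusions and restrictions, if these drugs are considered essential for patient management". Stability on the drug is a further condition.

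**The concern.** Two tables with the same introduction and the same purpose should hold the same drugs. They do not, and the eligibility criterion cites the shorter one. A site that checks eligibility from criterion 6 finds no washout for 22 drugs that section 6.5 says must be stopped 7 days to 4 months before dosing. A site that works from section 6.5 applies those washouts.

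This matters because section 1.2.1 gives a predicted QTc increase of 14.2 ms on osimertinib, and ECG abnormalities are part of a secondary endpoint (section 2.4.2). If sites apply different washouts, some patients may start with another QT-active drug only recently stopped. Their early ECG changes are then harder to interpret.

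**Working it through.** The plan states no count to reproduce, so the check compares the two tables row by row. Two entries printed without a comma (terfenadine terlipressin; azithromycin bepridil) are each read as two drugs. Spelling variants of bepridil, sultopride, pimozide and probucol are merged.

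| Washout | Table 4.1 | Section 6.5 | Only in 6.5 |
|---|---|---|---|
| 2 days | 15 | 15 | 0 |
| 7 days | 9 | 18 | 9 |
| 14 days | 5 | 12 | 7 |
| 3 weeks | 0 | 2 | 2 |
| 4 weeks | 3 | 3 | 0 |
| 6 weeks | 1 | 2 | 1 |
| 8 weeks | 1 | 1 | 0 |
| 4 months | 0 | 3 | 3 |
| 1 year | 2 | 2 | 0 |
| Total | 36 | 58 | 22 |

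**Direction of the difference.** No drug in Table 4.1 is missing from section 6.5, and 0 of the 36 shared drugs have a different washout. Table 4.1 is a strict subset. The omitted share is 22/58 = 38%.

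**The 22 drugs.**
- 7 days: cilostazol, flecainide, gatifloxacin, grepafloxacin, moxifloxacin, oxaliplatin, propofol, roxithromycin, sevoflurane.
- 14 days: azithromycin, citalopram, dronedarone, escitalopram, fluconazole, levomepromazine, levosulpiride.
- 3 weeks: donepezil, terodiline.
- 6 weeks: ibogaine.
- 4 months: astemizole, probucol, vandetanib.

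**Appendix 6.** All 22 are named there, so it shows that they are prohibited but not how long they must have been stopped.

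**Overlap with other exclusions.** Criterion 12 bars therapeutic oral or IV antibiotics within 2 weeks. Apart from prophylactic use, that matches or exceeds the section 6.5 period for azithromycin (14 days) and for gatifloxacin, grepafloxacin, moxifloxacin and roxithromycin (7 days). Criterion 8 bars chemotherapy within 14 days, which covers oxaliplatin (7 days). That leaves 22 − 5 − 1 = 16 drugs: four at 7 days, six at 14 days, two at 3 weeks, one at 6 weeks and three at 4 months.

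**Example.** A patient stops escitalopram 3 days before Day 1. Criterion 6 is passed, because the drug was stopped before the first day of treatment and Table 4.1 has no entry for it. Under section 6.5 the patient is 14 − 3 = 11 days short. For donepezil the shortfall is 21 − 3 = 18 days.

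**The protocol's own pointer.** Section 6.5 sends the reader to section 4.1 for lists of QTc-prolonging drugs, then names azithromycin and escitalopram as common supportive medicines of this kind. Neither is in Table 4.1.

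**Table 4.3.** Criterion 6 describes its drugs as contraindicated, with washouts. The table has eight drugs, permits all of them with caution and gives no washout. Appendix 6 prohibits all eight.

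**The case against.** The strongest reply is that the requirements are cumulative. Section 6.5 applies to every patient, Table 4.1 contradicts nothing in it, and a site that follows section 6.5 breaks no rule elsewhere. Both introductions warn that the list may not be exhaustive and send investigators to a website, and screening medicines must be checked there. This stands in part: the defect is an omission, and a careful site can comply with everything. It does not remove the gap, because criterion 6 names the tables to use for washouts and leaves out the fuller one, and the referral to the website puts no washout period into the protocol.

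A second reply is that the 3-week parenthesis in criterion 6 might cover QTc drugs as well as CYP3A4 inducers. It follows the inducers and most naturally belongs to them. If it covered both, the 7-day, 14-day and 3-week drugs would be dealt with and 16 − 4 − 6 − 2 = 4 drugs would remain. That reading would also clash with the 2-, 7- and 14-day rows of Table 4.1.

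Third, a reader might infer that criterion 7 and the Other TdP risk Categories paragraph flatly contradict each other. The documents do not establish that: the word notwithstanding can be read as giving the section 6.5 permission precedence. What stands is that criterion 7 does not refer to that permission, so a site reading the criteria alone would give a different enrolment answer.

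**Conclusion.** The point holds as a gap in washout timing. Of the 58 drugs with a section 6.5 washout, 22 have none in the table that criterion 6 cites, and about 16 remain once criteria 12 and 8 are applied. The figure of 16 assumes that the five agents named are used as therapeutic antibiotics and oxaliplatin as chemotherapy, and that the 3-week parenthesis belongs to the inducers. The documents do not allow an estimate of how many patients are affected.

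Three stronger readings are not supported:
- A reader might infer that a patient could start osimertinib while still taking one of the 22 drugs without breaching the exclusions. Appendix 6 and criterion 7 catch current use.
- A reader might infer that the tables give conflicting washouts for the same drug. None of the 36 shared drugs differs.
- A reader might infer that early QTc changes could not be attributed to osimertinib at all. Criterion 7 sets a screening limit on the mean of three ECGs, and further ECGs are scheduled on Days 1 and 15 of cycle 1. Confounding is possible in some patients, but attribution is not lost.

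The primary endpoint, major pathological response, is not affected. The point is still worth correcting, because a site following criterion 6 as written could dose a patient inside a washout that the same protocol requires. The Table 4.3 conflict with criterion 6 and Appendix 6 is separate and needs no assumption. The criterion 7 cross-reference is secondary.

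**What to change.** Reconcile Table 4.1, the section 6.5 table, Table 4.3 and Appendix 6 into one consistent list, with one status and one washout entry per drug (or an explicit statement that none applies). Cite that list in criterion 6 and in both sentences that now point to Table 3, and remove the duplicates. State in criterion 6 which drug group the 3-week parenthesis covers. Align criterion 7 with the Other TdP risk Categories paragraph, so that both give the same enrolment answer. Which washouts and rules apply is for the sponsor's clinical team.

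The cost is an amendment to wording and tables. Depending on the list kept, some patients may wait longer before starting treatment.

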Primary Objective	To evaluate the efficacy of osimertinib as neoadjuvant therapy in patients with surgically resectable EGFR-mutant NSCLC. The primary endpoint of the study will be MPR rate defined as $\leq 10\%$ viable tumor present histologically in the resected tumor specimen.

Secondary Objectives	
1. To evaluate the safety of osimertinib given as neoadjuvant therapy in early stage EGFR-mutant NSCLC patients
 
2. To evaluate whether neoadjuvant osimertinib treatment increases the frequency of tumors that are unresectable due to adverse events (AEs) or PD.
 
3. To evaluate secondary measures of clinical efficacy in early stage EGFR-mutant NSCLC patients treated with osimertinib induction therapy. Secondary endpoints of efficacy will include radiographic decrease in maximum tumor diameter, complete pathologic response rate, 5-year disease-free survival (DFS), and 5-year overall survival (OS).

Study Design	
This is a phase II multi-institution (UCSF and participating sites), single-arm, open-label clinical trial of neoadjuvant osimertinib in Stage I-IIIa EGFR-mutant lung cancer patients who are planning to undergo surgical resection of their lung cancer.
 
A total of 27 evaluable subjects will be enrolled in the study. This will provide 87% power to detect a MPR rate of 50% among patients receiving osimertinib induction therapy as compared to a null hypothesis response rate of 22%, which has been observed for neoadjuvant chemotherapy in unselected NSCLC populations [23, 24], at the 5% significance level.
 
Patients will receive the study drug for a minimum of 1 cycle prior to surgery (28 days). ORR will be determined by CT scan prior to surgery. Investigators will have the option to give a second cycle of study drug prior to surgery if clinically indicated.

Number of patients	27 patients will be enrolled.
Duration of Therapy	Patients may continue treatment for up to 70 days from the time of study entry.
Duration of Follow-up	Follow-up for individual participants will be up to 5 years.
Duration of study	The study will reach completion 48 months from the time the study opens to accrual.
Study Drugs	Osimertinib 80 mg per os (PO) daily

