#### 1.1.1 Treatment of early stage Non-Small Cell Lung Cancer

In patients with resectable stage I and II NSCLC, the standard of care is surgical resection, followed by consideration for adjuvant chemotherapy depending on pathologic staging. Adjuvant chemotherapy (with a platinum doublet) is recommended in patients with T3 or node positive disease, and should be considered in patients with T2 node negative disease in which there are other high risk features (such as poor differentiation, vascular invasion, size >4 cm, visceral pleural involvement, and wedge resection or unknown lymph node pathologic status). Concurrent or sequential chemoradiation should be considered in patients with positive margins after resection.

In patients with resectable stage IIIA disease, standard of care is to proceed with surgical resection followed by adjuvant chemotherapy, with radiation therapy if with positive margins or if found to have N2 nodal involvement upon pathologic staging. Patients with N2 positive stage IIIA disease are generally not felt to have upfront resectable disease and will instead undergo a course of neoadjuvant therapy (chemotherapy with or without radiation therapy) prior to reconsideration for surgical resection or upfront definitive chemoradiation therapy (National Comprehensive Cancer Network Guidelines – Non-Small Cell Lung Cancer, Version 7, 2017).

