**3.3.1 Inclusion Criteria**

1. Males and females ≥18 years of age.
2. Histologically or cytologically confirmed NSCLC, performed on a biopsy that occurred within the last 90 days. This biopsy can be deferred if the procedure is deemed to represent an unacceptable safety risk to the patient by the Principal Investigator and as long as the patient has a prior biopsy showing non-small cell lung cancer.
3. Documented activating EGFR mutation (Exon 19 deletion, T790M, or L858R) on tumor samples by Clinical Laboratory Improvement Amendments (CLIA)-approved test.
4. Patients treated with osimertinib or another EGFR TKI (including erlotinib, afatinib, gefitinib, & rociletinib) are eligible if they received no more than 28 days of treatment, and if there is no evidence of grade 2 or greater treatment adverse events possibly related to treatment with the EGFR TKI.
5. PET-CT (computerized tomography) within the last 60 days showing radiographic stage I to IIIa lung cancer (mediastinal staging biopsy is allowed but not required).
6. Brain magnetic resonance imaging (MRI) (or CT if contraindication to MRI) within the last 60 days showing no evidence of metastatic disease.
7. Documentation that the patient is a candidate for surgical resection of their lung cancer by an American Board of Thoracic Surgery certified surgeon.

8. The patient must have a tumor size  $\geq 1$  cm in its longest diameter.
9. Eastern Cooperative Oncology Group (ECOG) performance status of 0-1.
10. Any unresolved toxicities from prior therapy greater than CTCAE grade 1 at the time of starting study treatment, with the exception of alopecia and grade 2 prior platinum-therapy-related neuropathy is allowed
11. Adequate organ function:
  - Hepatic Function:
    - Aspartate aminotransferase (AST) and alanine aminotransferase (ALT)  $\leq 2.5$   $\times$  upper limit of normal (ULN).
    - Bilirubin  $\leq 1.5 \times$  ULN, (Patients with documented Gilbert's syndrome and conjugated bilirubin within the normal range may be allowed into the study. In this event, it will be documented that the patient was eligible based on conjugated bilirubin levels).
  - Electrolytes: Potassium, magnesium, and calcium within normal range, patients may receive supplements to meet this requirement.
  - Hematologic Function:
    - Leukocytes  $> 3,000/\text{mCL}$
    - Hemoglobin (Hgb)  $\geq 9$  g/dL, with no blood transfusions in the 28 days prior to study entry
    - Absolute neutrophil count  $> 1,500/\text{mCL}$

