### 8.3.2 Primary Analysis (or Analysis of Primary Endpoints)

MPR rate (primary endpoint) will be determined in patients who receive at least one dose of study drug.

Patients who receive one dose of study drug and become ineligible for surgery either because of disease progression or adverse event will be deemed not to have achieved MPR.

In patients who undergo surgical resection or their lung tumor resection specimens will be processed at the local institution following CAP and CLIA guidelines. Immediate sampling of the tumor and overnight fixation in 10% buffered formalin for paraffin embedding, usually within 20-24 hours after fixation. For histopathological evaluation, at least one sample per every 1-cm of diameter will be submitted for FFPE processing and pathology analysis. The local institutional study pathologist will assess each case for MPR, using percentage of viable tumor cells (cutoff as + MPR is  $\leq 10\%$  of viable tumor cells) as has been reported [24]. The pathological response should be reported as average percentage of viable tumor cells by slide examined.

Pathology slides (H&E and IHC and special stains) will be forwarded to the designated central pathologists for the study and MPR will be determined as described above.

In order to more fully evaluate the specimens associated with this trial, the central review pathologists will score the material using criteria as follows:

Pathological CR: Residual viable tumor: 0% MPR: Residual viable tumor:  $\leq 10\%$

Pathological response (not meeting major response criteria) 11-49% residual viable tumor. No pathological response: 50% or greater residual viable tumor.

Predominant reaction type: Necrosis, Fibrosis

**Tumors that exhibit  $\leq 10\%$  viable tumor will meet the criteria for an MPR as has been previously described [24].** The MPR rate will be reported with 95% confidence intervals.

As needed, a sub-set of tissues will be independently evaluated by both pathologists for assessment of inter-pathologist reproducibility for this scoring.

Whenever possible, the following will be included:

- Concurrent submission of pre-treatment biopsy or FNA sample. This can help inform pathologic evaluation in that pre-treatment necrosis can be assessed, within the context of potential sampling bias.
- Whenever feasible, all post-treatment surgical tumor samples will be submitted for pathologic examination (full lesion block-in), after tissue procurements have been completed.

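### Eligibility does not require the study tumor to be untreated, so any response left by earlier chemotherapy, immunotherapy or thoracic radiation would be counted as osimertinib MPR

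*Combined protocol and SAP*

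**What the plan says.** **Eligibility (3.3.1 and 3.3.2).** Exclusion 8 opens with "Treatment with prohibited medications (concurrent anticancer therapy including chemotherapy, radiation, hormonal treatment" and ends with "immunotherapy) ≤ 14 days prior to treatment with osimertinib". It names no tumor and no line of therapy. Inclusion 4 limits earlier EGFR TKI exposure: such patients "are eligible if they received no more than 28 days of treatment" and had no relevant toxicity. Chemotherapy, immunotherapy and radiation have no matching limit. Exclusion 5 requires that "all chemotherapy for prior malignancy was completed >12 months prior", but this concerns a different cancer that has been completely treated. Inclusion 10, on unresolved toxicity, says that "grade 2 prior platinum-therapy-related neuropathy is allowed".

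**Clinical background (1.1.1).** Patients with N2-positive stage IIIA disease are generally not taken straight to surgery. They "will instead undergo a course of neoadjuvant therapy (chemotherapy with or without radiation therapy) prior to reconsideration for surgical resection", or have definitive chemoradiation. Radiographic stage IIIA is eligible under inclusion 5.

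**Primary analysis (8.3.2).** MPR is assessed in all patients who receive at least one dose, by percentage of viable tumor in the resected specimen. Dosed patients who "become ineligible for surgery either because of disease progression or adverse event will be deemed not to have achieved MPR". Nothing is said about treatment of the tumor before entry. A pre-treatment sample is submitted where possible, without a rule for adjusting the score.

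**Benchmark (Abstract, Study Design).** The comparison is with a "null hypothesis response rate of 22%, which has been observed for neoadjuvant chemotherapy in unselected NSCLC populations".

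**The concern.** The primary endpoint is a single histological reading at resection. It measures how much viable tumor remains, not which treatment removed the rest. If a patient's tumor had chemotherapy or radiation shortly before entry, the specimen reflects both that treatment and osimertinib, and 8.3.2 attributes the whole result to osimertinib.

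The choice of null makes this more than a labelling issue. Because 22% is a chemotherapy MPR rate, response produced by earlier chemotherapy would help the trial beat a chemotherapy benchmark. The bias is toward declaring success. With 27 patients and no control arm, nothing in the design would reveal it.

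Sections 3.3.1 and 3.3.2 contain no substitute safeguard:

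- Exclusion 3 removes patients with radiation pneumonitis that needed steroids, not radiation as such.
- Exclusion 5 is about another malignancy.
- Exclusion 20 covers investigational products from another study.
- The requirements for a recent biopsy and PET-CT do not require an untreated tumor.
- If the word concurrent in exclusion 8 is read narrowly, the criterion bars less, not more.

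**Working it through.** **Inputs from the documents.** N = 27 evaluable; null MPR 22%; alternative 50%; 5% significance level, sidedness not stated; stated power 87% (8.1.1 and Abstract). Section 8.3.2 reports the MPR rate with a 95% confidence interval and gives no explicit success rule.

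**Step 1. Reproduce the plan's power.** Let X be the number of MPRs among 27, binomial.

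- Success if X ≥ 11: P(X ≥ 11 | 0.22) = 0.0221 and P(X ≥ 11 | 0.50) = 0.876, which matches the stated 87%.
- Success if X ≥ 10: P(X ≥ 10 | 0.22) = 0.0549, above 5%, with power 0.939.
- The exact two-sided 5% test also has its upper cut-off at 11.
- The exact (Clopper-Pearson) 95% lower limit is 22.4% at 11/27 and 19.4% at 10/27, so 11 is also the first count whose interval lies above 22%.

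The rule X ≥ 11 is therefore inferred from the stated power; the plan does not write it down.

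**Step 2. Model for pretreated patients (assumptions).** Let k of the 27 have had earlier treatment of the study tumor. Set osimertinib's own MPR probability at the null, 0.22. Let q be the probability that the earlier treatment alone leaves a tumor meeting the MPR definition, acting independently of osimertinib. Then

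P(MPR | pretreated) = 1 − (1 − 0.22)(1 − q).

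- q = 0.10 (assumed): 1 − 0.78 × 0.90 = 0.298.
- q = 0.22 (the plan's chemotherapy benchmark): 1 − 0.78 × 0.78 = 0.392.

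**Step 3. Chance of false success.** X is the sum of a binomial with k patients at the probability above and a binomial with 27 − k patients at 0.22. The expected MPR rate is [k × P(MPR | pretreated) + (27 − k) × 0.22] / 27.

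| Pretreated k | Expected MPR, q = 10% | P(X ≥ 11), q = 10% | Expected MPR, q = 22% | P(X ≥ 11), q = 22% |
|---|---|---|---|---|
| 0 | 22.0% | 2.2% | 22.0% | 2.2% |
| 3 | 22.9% | 2.9% | 23.9% | 3.8% |
| 4 | 23.2% | 3.1% | 24.5% | 4.5% |
| 5 | 23.4% | 3.4% | 25.2% | 5.3% |
| 8 | 24.3% | 4.3% | 27.1% | 8.4% |

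With q = 22% the nominal 5% level is first passed at 5 pretreated patients of 27. With q = 10% it is not passed at 8.

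**Step 4. Which q is plausible?** Entry requires a tumor of at least 1 cm, NSCLC confirmed on a biopsy within 90 days, and a research biopsy within 30 days. The biopsies can be deferred for safety, and the research biopsy also when no lesion can be reached. Most pretreated entrants would thus have demonstrable residual tumor, so they are not a random draw from all chemotherapy-treated tumors. The value 22% is probably high for them. The documents do not give the right figure, hence the range.

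**The case against.** The strongest reply is that the documents do not show such patients are expected.

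- A reader might take the platinum-neuropathy allowance in inclusion 10 as proof that they are. It is not: exclusion 5 admits patients whose platinum was given for another, completely treated cancer.
- The remark on previously irradiated lesions in 7.2.2 sits in generic response-criteria text that also mentions liver metastases, inflammatory breast disease and PSA.
- Recording prior treatments at screening is routine.
- The accrual estimate in 8.1.3 counts new early-stage patients.
- A patient who has finished induction and is fit for resection would have to postpone surgery for at least 28 days of osimertinib. That is possible, but nothing in the documents suggests it is common.

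All of this stands. It limits how often the problem would occur; it does not close the gap.

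A reader might also infer two stronger claims. The first is a large inflation after chemoradiation. With q = 40%, the same calculation gives 5.5%, 9.3% and 18.2% for 3, 5 and 8 patients, but the documents contain no such rate and no such count. The second is an equal leak after entry, where a patient stops osimertinib, receives other therapy and is later resected. Section 6.5 takes such a patient off the treatment portion, surgery is tied to within 14 days of the final scan, and 8.3.2 already counts patients who lose eligibility for surgery through progression or an adverse event as non-MPR. What remains is a missing clarification.

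**Conclusion.** The gap is real but conditional. As written, a patient whose current tumor had chemotherapy, immunotherapy or thoracic radiation can enter once more than 14 days have passed, and any MPR would count for osimertinib against a chemotherapy-derived null.

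The table's range of 2.9% to 8.4% for 3 to 8 pretreated patients, against a design size of 2.2%, rests on four assumptions: the inferred rule of 11 of 27, a true osimertinib rate of 22%, independent effects, and the number of pretreated patients, for which the documents offer no estimate. The upper part of the range also needs a chemotherapy-alone rate that the entry requirements make unlikely.

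Severity is moderate. The plan does not establish that the primary result will be biased, but it permits the bias and provides no way to detect or handle it.

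**What to change.** 1. In 3.3.2, state that prior systemic anticancer therapy for the current lung cancer (apart from the EGFR TKI exposure addressed in inclusion 4) and prior thoracic radiation for it are excluded. Keep the 14-day rule for other uses. If any such patient has already enrolled, report the primary MPR rate with and without them.
2. As a minor clarification in 8.3.2, state that a dosed patient who receives non-protocol anticancer therapy before resection counts as not having achieved MPR.

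The cost is two sentences in an amendment. A few pretreated N2 stage IIIA patients would become ineligible. N = 27, the cut-off of 11 and the exact power of 87.6% stay as they are.
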